#### **9.2.6 Dyskinesia measured by a wearable dyskinesia assessment device**

Change from baseline in dyskinesia measured by the Kinesia 360 (Great Lakes Neurotechnologies, Inc) wearable dyskinesia assessment system to Visit 6 (Day 28) and Visit 7 (Day 42) respectively will be summarized using descriptive statistics. In this analysis, the mean of all measurements prior to Visit 2 and the mean of all measurements from 4\*24 hours prior to and up until Visit 6 and 7 respectively for each patient will be used as input data. However, recorded episodes of less than 30 minutes have not been used in the analysis. Furthermore, if there is not at least 8 hours of valid data according to the rules stipulated above for a specific patient and visit, the corresponding timepoint is set to missing for Kinesia 360 data and hence, not used in the analysis. The Kinesia 360 variable “Dyskinesia detect” will be analyzed this way and reported in the CSR. Dyskinesia detect will be analysed using inferential statistics as described under 9.2.1 above.

### **9.3 Analysis of tertiary/exploratory endpoints**

#### **9.3.1 King's Parkinson's Disease Pain Scale (KPPS) total score**

Change from baseline in the KPPS individual pain domain scores and total score to Visit 6 (Day 28) and Visit 7 (Day 42) respectively will be summarized using descriptive statistics. KPPS individual pain domain scores and total score will be analysed using inferential statistics as described under 9.2.1 above.

#### **9.3.2 Parkinson's Disease Questionnaire (PDQ39) total score**

The PDQ39 questionnaire assesses how often people affected by PD experience difficulties across 8 dimensions of daily living. The standard PDQ39 assesses quality of life over the previous month. In this study the initial time period assessed at the Baseline Visit will be the previous month, with subsequent assessments for the intervening period since the last clinic visit (about 3 weeks).

The 8 quality of life dimensions covered in the questionnaire are:

- Mobility (10 items #1-10)
- ADL (6 items #11-16)

- Emotional Well Being (6 items #17-22)
- Stigma (4 items #23-26)
- Social Support (3 items #27-29)
- Cognition (4 items #30-33)
- Communications (3 items #34-36)
- Bodily Discomfort (3 items #37-39)

Individual items are rated by the patient on a categorical scale which will be re-coded to a scale of 0 to 4.

Change from baseline in the PDQ39 quality of life dimensions scores and total score to Visit 6 (Day 28) and Visit 7 (Day 42) respectively will be summarized using descriptive statistics. In this analysis each quality-of-life dimensions will be weighted to a scale of 0 to 100 using the formula

Calculated dimension score = total registered score point for the dimension \* 100 / maximum possible score points for the dimension

, to allow each dimension to have an equal impact on the total score. PDQ39 quality of life dimensions scores and total score will be analysed using inferential statistics as described under 9.2.1 above.

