#### **11.4.2 *Parkinson's Disease Questionnaire (PDQ39)***

The PDQ39-item patient reported outcome of health status and quality of life and is the most frequently used disease-specific health status measure for PD. The questionnaire assesses how often people affected by PD experience difficulties across 8 dimensions of daily living. The standard PDQ39 assesses quality of life over the previous month. In this study the initial time period assessed at the Baseline Visit will be the previous month, with subsequent assessments for the intervening period since the last clinic visit (about 3 weeks).

The 8 quality of life dimensions covered in the questionnaire are:

- Mobility (10 items #1-10)
- ADL (6 items #11-16)
- Emotional Well Being (6 items #17-22)
- Stigma (4 items #23-26)
- Social Support (3 items #27-29)
- Cognition (4 items #30-33)
- Communications (3 items #34-36)
- Bodily Discomfort (3 items #37-39)

Individual items are rated by the patient on a scale of 0 to 5. Dimension scores are calculated on a scale of 0 to 100. The total score and individual dimension scores will be assessed for change from baseline.

For timing of assessments, refer to Table 8.1-1.

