## 5.9 Handling of dropouts, missing data and outliers

Outliers will be included in summary tables and listings and will not be handled separately in any analyses. Generally, no imputation of data will be performed. However, in case of a substantial amount of missing data, judged to affect analyses conclusions related to secondary and exploratory endpoints, imputation methods might be considered or alternative analysis approaches, for example analysing mean scores instead of total scores.

In case of missing start and stop times of AEs that cannot be investigated further, missing data will be imputed according to a worst-case scenario. That is, start time will be imputed as the closest time point post first intake of IMP and end time as 23:59, resulting in the longest possible treatment emergent duration of the AE.

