### 10.2.3 Secondary endpoint(s)

#### 10.2.3.1 Unified Dyskinesia Rating Scale (UDysRS) total score

**Table UD 1 UDysRS total score for all Parts (Full analysis set)**

Result category	Assessment timepoint		NLX-112 (N=XX)	Placebo (N=XX)	Total (N=XX)
Measured value	[Assessment timepoint 1]	n	xx	xx	xx
		Mean (SD)	x.xx (x.xx)	x.xx (x.xx)	x.xx (x.xx)
		Median (Min, Max)	x.xx (x.x, x.x)	x.xx (x.x, x.x)	x.xx (x.x, x.x)
	[Assessment timepoint 2]	n	xx	xx	xx
		...	...	...	...
Absolute change from baseline	[Assessment timepoint 2]	n	xx	xx	xx
		Mean (SD)	x.xx (x.xx)	x.xx (x.xx)	x.xx (x.xx)
		Median (Min, Max)	x.xx (x.x, x.x)	x.xx (x.x, x.x)	x.xx (x.x, x.x)
	[Assessment timepoint 3]	LMM a p-value	xxxxx b	xxxxx c	xxxxx d
		n	xxxxx	xxxxx	xxxxx
		...	...	...	...
Relative change from baseline (%)	[Assessment timepoint 2]	n	xx	xx	xx
		Mean (SD)	x.xx (x.xx)	x.xx (x.xx)	x.xx (x.xx)
		Median (Min, Max)	x.xx (x.x, x.x)	x.xx (x.x, x.x)	x.xx (x.x, x.x)
	[Assessment timepoint 3]	n	xxxxx	xxxxx	xxxxx
		...	...	...	...

a) Linear mixed model (LMM) with treatment, visit and the interaction treatment\*visit as fixed categorical effects and subject within treatment as a random effect. The baseline value of the dependent variable has been included in the model as a continuous covariate. Kenward-Roger's approximation for degrees of freedom will be used.

b) p-value for the difference between NLX-112 at the assessment timepoint and at baseline.

c) p-value for the difference between placebo at the assessment timepoint and at baseline.

d) p-value for the difference between NLX-112 and placebo absolute change from baseline at the assessment timepoint.

Data based on the Full analysis set. The session marked as most severe for Part III and IV have been used. For Part III, the highest score for each individual questionnaire item has been used. All UDysRS item scores for Part I, II, III and IV have been summarized pre patient and assessment timepoint and used as input data to the table. N: Number of observations. SD: Standard deviation. NC: Not calculated - number of evaluable observations less than 3. NA: Not available - no evaluable observations. SAS program: [PROGRAM NAME].sas. Run by: [USERNAME] YYYY-MM-DDTHH:MM:SS. Data extracted at: YYYY-MM-DDTHH:MM:SS

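### SAP 9.3.2 gives no rule for unanswered PDQ39 items, and its formula, applied literally, scores a blank as 0

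*SAP*

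**What the plan says.** SAP 9.3.2 computes each dimension score as the "total registered score point for the dimension", multiplied by 100 and divided by the "maximum possible score points for the dimension". The stated purpose is to give the dimensions equal influence on the total, but the section does not say whether the total is their sum or their mean. On item coding it says: "Individual items are rated by the patient on a categorical scale which will be re-coded to a scale of 0 to 4".

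The section does not mention unanswered items. It has no denominator restricted to answered items, no minimum number of answers and no instruction to set a dimension to missing. By contrast, SAP 9.2.3 (diary) and 9.2.6 (Kinesia 360) each set a timepoint to missing when less than 8 hours of data are available.

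The general rule in SAP 5.9 is: "Generally, no imputation of data will be performed". It then leaves room, when missing data are substantial and judged to affect conclusions, for imputation or for mean scores in place of totals. Protocol 17.1 rules out imputation without qualification.

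**The concern.** The numerator depends on what the patient answered, while the denominator, read at face value, is a fixed property of the dimension. A program written directly from the formula would therefore give a blank item the lowest code. SAP 9.3.2 describes the questionnaire as asking how often difficulties occur, so 0 is by inference the best answer, although the codes are not labelled.

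An item answered at baseline and left blank at Day 28 or Day 42 would then look like improvement, and the reverse would look like worsening. The dimension scores are named endpoints (Protocol 7.3.1) and each is tested under SAP 9.2.1, so the error is not confined to a total in which it would be diluted. Two programmers could also derive different scores from the same data while both following the SAP.

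**Working it through.** **Inputs.** Item range 0 to 4 (SAP 9.3.2). Protocol 11.4.2 instead says "Individual items are rated by the patient on a scale of 0 to 5"; the SAP range is used here because the formula belongs to the SAP. Items per dimension (SAP 9.3.2): 10 for Mobility; 6 for ADL and for Emotional Well Being; 4 for Stigma and for Cognition; 3 for Social Support, Communications and Bodily Discomfort. Check: 10 + 2×6 + 2×4 + 3×3 = 39. Arm sizes: about 16 and 8 (SAP 4.3). The documents contain no worked PDQ39 score to reproduce. With every item answered, the formula runs correctly from 0 to 4k×100/(4k) = 100.

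**One blank item, literal reading.** Let S be the points from the other k − 1 items and a the answer the patient would have given to the blank one.

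- Score with all items answered: 100(S + a)/(4k)
- Score by the formula with the blank: 100S/(4k)
- Difference: −100a/(4k) = −25a/k

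The shift does not depend on the other answers.

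| Items k | Dimensions | a = 1 | a = 2 | a = 4 |
|---|---|---|---|---|
| 3 | 3 | −8.3 | −16.7 | −33.3 |
| 4 | 2 | −6.25 | −12.5 | −25.0 |
| 6 | 2 | −4.2 | −8.3 | −16.7 |
| 10 | 1 | −2.5 | −5.0 | −10.0 |

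At a = 0 the shift is zero. If the same item is blank at both visits, the error in the change is −25(a at follow-up − a at baseline)/k, which vanishes when the true answer has not moved.

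**Arm mean.** One patient with a = 2 in a 3-item dimension moves the raw arm mean by 16.7/8 = 2.1 points on placebo or 16.7/16 = 1.0 on NLX-112.

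**Total.** If the total is the mean of the eight dimensions (an assumption), one blank at a = 2 moves a patient's total by 16.7/8 = 2.1 points in a 3-item dimension, down to 5.0/8 = 0.6 in the 10-item one.

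**Would the plan catch it?** The per-protocol sensitivity analysis in SAP 9.2.1 keeps patients with no missing value of the dependent variable. A dimension score computed despite a blank is not missing, so that patient stays in. The switch to mean scores in SAP 5.9 is discretionary, has no threshold and is aimed at substantial missingness, not at one or two blanks.

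**After the change.** With the denominator 4(k − 1), a patient who would answer 2 throughout and skips one item scores 50.0 in every dimension, so the error is zero. That relies on the blank resembling the patient's other answers. With k = 3, two answers of 2 and a true blank of 0, the correct score is 4×100/12 = 33.3 and pro-rating gives 4×100/8 = 50.0.

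**The case against.** The strongest reply is that the SAP never says a blank scores 0. A reader might infer from the formula that every missing PDQ39 answer will be counted as no problem. The documents do not support that: they are silent, and leaving the dimension missing fits the no-imputation statements at least as well. SAP 5.9 also allows another approach if missingness proves substantial. This stands, and it limits the point to an unspecified rule whose literal application goes wrong.

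Second, blanks may be rare. Protocol 16.1 to 16.3 describe eCRF completeness checks, recording of items not done, and monitor queries. These should reduce blanks, but they do not tell the programmer how to score one that remains.

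Third, the arm-mean figures are raw means. The planned model adjusts for baseline, which could dampen an error caused by a baseline blank, and no SD is given against which to judge 2.1 points. Both are fair.

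Fourth, PDQ39 is exploratory, tests are unadjusted (SAP 5.8), and SAP 5.1 treats significant findings as indicative. No primary or secondary conclusion depends on it.

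Fifth, pro-rating is itself a mild form of imputation. That is correct, so it must be declared if adopted.

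A reader might also carry the point over to the UDysRS total, the first-listed secondary endpoint, because the Table UD 1 footnote says "All UDysRS item scores for Part I, II, III and IV have been summarized pre patient and assessment timepoint". That sentence describes adding items and does not say how blanks are treated. Protocol Table 8.2-1 assigns UDysRS Parts III and IV to the investigator, so patient skipping is a weak analogy there. The PDQ39 finding does not establish a fault in the other summed scales.

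**Conclusion.** The point holds as a gap in the scoring rule. Followed literally, SAP 9.3.2 understates a dimension by 25a/k points for each blank item: 5.0 to 16.7 points at an answer level of 2, and up to 33.3 in a 3-item dimension. The three 3-item and two 4-item dimensions, five of the eight, are the most exposed. Neither SAP 5.9 nor the complete-case analysis would reliably catch it.

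The size rests on the literal reading of the formula, the 0–4 coding, one blank item with a true answer above 0, and a missing pattern that differs between baseline and follow-up. How often this would occur cannot be judged from the documents. The consequence is limited to exploratory quality-of-life results, but the remedy is cheap enough that it should be made.

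**What to change.** Before database lock, amend SAP 9.3.2 in one of two ways:

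- score each dimension as 100 × (sum of answered items) / (4 × number of answered items), and set it to missing if fewer than a prespecified number of its items, for example half, are answered; or
- set any dimension with a blank item to missing.

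Define the total as the mean of the eight dimension scores, missing if any dimension is missing. If pro-rating is chosen, record it as a stated exception to the no-imputation wording in SAP 5.9 and Protocol 17.1. State that the 0–4 coding applies in place of the 0–5 range in Protocol 11.4.2, because the factor 4 depends on it.

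Do not extend one pro-rating rule to all the investigator-rated summed scales without separate justification; it assumes that items are interchangeable.

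The cost is a few lines of SAP text and a small change to the derivation program. The statistical price is a mild person-mean assumption under the first option, or the loss of a few scores under the second.

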### **9.3.3 Hospital Anxiety Depression Scale (HADS)**

Change from baseline in the HADS to Visit 6 (Day 28) and Visit 7 (Day 42) respectively will be summarized using descriptive statistics. Summaries will be made for the total anxiety score and total depression score respectively. HADS will be analysed using inferential statistics as described under 9.2.1 above.

### **9.3.4 International Consultation on Incontinence Questionnaire Overactive Bladder Module (ICIQ-OAB) total score**

Change from baseline in the ICIQ-OAB total score to Visit 6 (Day 28) and Visit 7 (Day 42) respectively will be summarized using descriptive statistics. In this analysis, individual ICIQ-OAB answers will be re-coded to a scale of 0-4. ICIQ-OAB total score will be analysed using inferential statistics as described under 9.2.1 above.

### **9.3.5 Epworth Sleepiness Scale (ESS)**

Change from baseline in the ESS total score to Visit 6 (Day 28) and Visit 7 (Day 42) respectively will be summarized using descriptive statistics. ESS total score will be analysed using inferential statistics as described under 9.2.1 above.

## **9.4 Description of study population**

Other study population/demographics data will be presented in listings and summarized descriptively as described in section 10 below.

## 10 DATA DISPLAY PLAN

Tables and figures will only be generated if sufficient data, with sufficient variability exist to justify specific output being produced.

## 10.2 Study tables

### 10.2.1 Demographic data

**Table DM 1 Baseline characteristics, demographics and estimated compliance (Full analysis set)**

Assessment (unit)		NLX-112 (N=XX)	Placebo (N=XX)	Total (N=XX)
Age (years)	n	x	x	x
	Mean (SD)	xx.x (xx.x)	xx.x (xx.x)	xx.x (xx x)
	Median (Min, Max)	xx.x (xx, xx)	xx.x (xx, xx)	xx.x (xx, xx)
Height (cm)	n	x	x	x
	Mean (SD)	xxx.x (xx.x)	xxx x (xx.x)	xxx.x (xx.x)
	Median (Min, Max)	xxx.x (xxx, xxx)	xxx x (xxx, xxx)	xxx.x (xxx, xxx)
Weight (kg)	n	x	x	x
	Mean (SD)	xx.xx (xx.xx)	xx.xx (xx.xx)	xx.xx (xx.xx)
	Median (Min, Max)	xx.xx (xx.x, xx.x)	xx.xx (xx.x, xx.x)	xx.xx (xx.x, xx.x)
Body Mass Index (kg/m2)	n	x	x	X
	Mean (SD)	xx.xx (xx.xx)	xx.xx (xx.xx)	xx.xx (xx.xx)
	Median (Min, Max)	xx.xx (xx.x, xx.x)	xx.xx (xx.x, xx.x)	xx.xx (xx.x, xx.x)
Sex	Female	xx (xx%)	xx (xx%)	xx (xx%)
	Male	xx (xx%)	xx (xx%)	xx (xx%)
Ethnicity	Hispanic or latino	xx (xx%)	xx (xx%)	xx (xx%)
	Not hispanic or latino	xx (xx%)	xx (xx%)	xx (xx%)
	Not reported	xx (xx%)	xx (xx%)	xx (xx%)
	Unknown	xx (xx%)	xx (xx%)	xx (xx%)
Race	American Indian or Alaska Native	xx (xx%)	xx (xx%)	xx (xx%)
	Asian	xx (xx%)	xx (xx%)	xx (xx%)
	Black or African American	xx (xx%)	xx (xx%)	xx (xx%)

Assessment (unit)		NLX-112 (N=XX)	Placebo (N=XX)	Total (N=XX)
	Native Hawaiian or Other Pacific Islander	xx (xx%)	xx (xx%)	xx (xx%)
	White	xx (xx%)	xx (xx%)	xx (xx%)
Compliance (%)	n	x	x	x
	Mean (SD)	xx.x (xx.x)	xx.x (xx.x)	xx.x (xx x)
	Median (Min, Max)	xx.x (xx, xx)	xx.x (xx, xx)	xx.x (xx, xx)

Data based on the Full analysis set. N: number of subjects in treatment group. Mean values and percentages are based on n. n: Number of observations. SD: Standard deviation. SAS program: [PROGRAM NAME].sas. Run by: [USERNAME] YYYY-MM-DDTHH:MM:SS. Data extracted at: YYYY-MM-DDTHH:MM:SS

**Table DS 1 Subject disposition (All subjects)**

	Total (N=XXX)
Screened subjects	xxx
Withdrawn prior to dose	xxx
Reason for withdrawal prior to dose	
--- Reason 1	xxx
--- Reason 2	xxx
--- ...	xxx
Subjects included in study	xxx
Allocated to arm	
--- NLX-112	xxx
--- Placebo	xxx
Withdrawn subjects	
--- [REASON 1]	xxx
--- [REASON 2]	xxx
--- ...	xxx
Completed subjects	xxx
Included in Full analysis set	xxx

	Total (N=XXX)
Included in Per protocol set	xxx
Subjects at each visit	
--- Visit 1	xxx
--- Visit 2	xxx
--- Visit 3	xxx
--- Visit 4	xxx
--- Visit 5	xxx
--- Visit 6	xxx
--- Visit 7	xxx
--- Visit 8	xxx
--- Visit 9	xxx

---

Data based on All subjects. SAS program: [PROGRAM NAME].sas. Run by: [USERNAME] YYYY-MM-DDTHH:MM:SS. Data extracted at: YYYY-MM-DDTHH:MM:SS

**Table MH 1 Medical/psychiatric history events by system organ class and preferred term (Full analysis set)**

System organ class Preferred term	NLX-112 (N=XX)	n (%)	m	Placebo (N=XX)	n (%)	m	Total (N=XX)	n (%)	m
Total	xx (xx%)	xx	xx	xx (xx%)	xx	xx	xx (xx%)	xx	xx
[SOC 1]	xx (xx%)	xx	xx	xx (xx%)	xx	xx	xx (xx%)	xx	xx
[SOC 1 PT 1]	xx (xx%)	xx	xx	xx (xx%)	xx	xx	xx (xx%)	xx	xx
[SOC 1 PT 2]	xx (xx%)	xx	xx	xx (xx%)	xx	xx	xx (xx%)	xx	xx
[SOC 1 PT ...]	xx (xx%)	xx	xx	xx (xx%)	xx	xx	xx (xx%)	xx	xx
[SOC 2]	xx (xx%)	xx	xx	xx (xx%)	xx	xx	xx (xx%)	xx	xx
[SOC 2 PT 1]	xx (xx%)	xx	xx	xx (xx%)	xx	xx	xx (xx%)	xx	xx
[SOC 2 PT 2]	xx (xx%)	xx	xx	xx (xx%)	xx	xx	xx (xx%)	xx	xx
[SOC 2 PT ...]	xx (xx%)	xx	xx	xx (xx%)	xx	xx	xx (xx%)	xx	xx
[SOC ...]	xx (xx%)	xx	xx	xx (xx%)	xx	xx	xx (xx%)	xx	xx
[SOC ... PT 1]	xx (xx%)	xx	xx	xx (xx%)	xx	xx	xx (xx%)	xx	xx
[SOC ... PT 2]	xx (xx%)	xx	xx	xx (xx%)	xx	xx	xx (xx%)	xx	xx
[SOC ... PT ...]	xx (xx%)	xx	xx	xx (xx%)	xx	xx	xx (xx%)	xx	xx

Data based on the Full analysis set. n, number of subjects. m, number of events. Percentages are based on the number of subjects in the treatment period. The following events are coded with multiple terms and are represented as separate events in tables and listings: '[MH TERM 1], [MH TERM 2]'. See listings for detailed information. SAS program: [PROGRAM NAME].sas. Run by: [USERNAME] YYYY-MM-DDTHH:MM:SS. Data extracted at: YYYY-MM-DDTHH:MM:SS

**Table CM 1 Prior medications by ATC levels 1, 3 and 5 (Full analysis set)**

ATC Name Level 1 ATC Name Level 3 ATC Name Level 5	NLX-112 (N=XX)	n (%)	m	Placebo (N=XX)	n (%)	m	Total (N=XX)	n (%)	m
Total	xx (xx%)	xx	xx	xx (xx%)	xx	xx	xx (xx%)	xx	xx
[L1 1]	xx (xx%)	xx	xx	xx (xx%)	xx	xx	xx (xx%)	xx	xx
[L1 1 L3 1 L5 1]	xx (xx%)	xx	xx	xx (xx%)	xx	xx	xx (xx%)	xx	xx
[L1 1 L3 2 L5 1]	xx (xx%)	xx	xx	xx (xx%)	xx	xx	xx (xx%)	xx	xx
[L1 1 L3 ...L5 1]	xx (xx%)	xx	xx	xx (xx%)	xx	xx	xx (xx%)	xx	xx
[L1 2]	xx (xx%)	xx	xx	xx (xx%)	xx	xx	xx (xx%)	xx	xx
[L1 2 L3 1 L5 1]	xx (xx%)	xx	xx	xx (xx%)	xx	xx	xx (xx%)	xx	xx
[L1 2 L3 2 L5 1]	xx (xx%)	xx	xx	xx (xx%)	xx	xx	xx (xx%)	xx	xx
[L1 2 L3 ...L5 1]	xx (xx%)	xx	xx	xx (xx%)	xx	xx	xx (xx%)	xx	xx
[L1 ...]	xx (xx%)	xx	xx	xx (xx%)	xx	xx	xx (xx%)	xx	xx
[L1 ... L3 1 L5 1]	xx (xx%)	xx	xx	xx (xx%)	xx	xx	xx (xx%)	xx	xx
[L1 ... L3 2 L5 1]	xx (xx%)	xx	xx	xx (xx%)	xx	xx	xx (xx%)	xx	xx
[L1 ... L3 ...L5 1]	xx (xx%)	xx	xx	xx (xx%)	xx	xx	xx (xx%)	xx	xx

Data based on the Full analysis set. n, number of subjects. m, number of events. Percentages are based on the number of subjects in the treatment period. The following records are coded with multiple terms and are represented as separate events in tables and listings: '[CM TERM 1], [CM TERM 2]'. See listings for detailed information. SAS program: [PROGRAM NAME].sas. Run by: [USERNAME] YYYY-MM-DDTHH:MM:SS. Data extracted at: YYYY-MM-DDTHH:MM:SS

**Table CM 2 Concomitant medications by ATC levels 1, 3 and 5 (Full analysis set)**

ATC Name Level 1 ATC Name Level 3 ATC Name Level 5	NLX-112 (N=XX)	Placebo (N=XX)	Total (N=XX)			
	n (%)	m	n (%)	m	n (%)	m
Total	xx (xx%)	xx	xx (xx%)	xx	xx (xx%)	xx
[L1 1]	xx (xx%)	xx	xx (xx%)	xx	xx (xx%)	xx
[L1 1 L3 1 L5 1]	xx (xx%)	xx	xx (xx%)	xx	xx (xx%)	xx
[L1 1 L3 2 L5 1]	xx (xx%)	xx	xx (xx%)	xx	xx (xx%)	xx
[L1 1 L3 ...L5 1]	xx (xx%)	xx	xx (xx%)	xx	xx (xx%)	xx
[L1 2]	xx (xx%)	xx	xx (xx%)	xx	xx (xx%)	xx
[L1 2 L3 1 L5 1]	xx (xx%)	xx	xx (xx%)	xx	xx (xx%)	xx
[L1 2 L3 2 L5 1]	xx (xx%)	xx	xx (xx%)	xx	xx (xx%)	xx
[L1 2 L3 ...L5 1]	xx (xx%)	xx	xx (xx%)	xx	xx (xx%)	xx
[L1 ...]	xx (xx%)	xx	xx (xx%)	xx	xx (xx%)	xx
[L1 ... L3 1 L5 1]	xx (xx%)	xx	xx (xx%)	xx	xx (xx%)	xx
[L1 ... L3 2 L5 1]	xx (xx%)	xx	xx (xx%)	xx	xx (xx%)	xx
[L1 ... L3 ...L5 1]	xx (xx%)	xx	xx (xx%)	xx	xx (xx%)	xx

Data based on the Full analysis set. n, number of subjects. m, number of events. Percentages are based on the number of subjects in the treatment period. The following records are coded with multiple terms and are represented as separate events in tables and listings: '[CM TERM 1], [CM TERM 2]'. See listings for detailed information. SAS program: [PROGRAM NAME].sas. Run by: [USERNAME] YYYY-MM-DDTHH:MM:SS. Data extracted at: YYYY-MM-DDTHH:MM:SS

## 10.2.2 Primary endpoint(s)

### 10.2.2.1 Adverse events

**Table AE 1 Overview of adverse events (Full analysis set)**

	N LX-112 (N=XX)	Placebo (N=XX)		Total (N=XX)		
	n (%)	m	n (%)	m	n (%)	m
Any AE	xx (xx%)	xx	xx (xx%)	xx	xx (xx%)	xx
Any SAE	xx (xx%)	xx	xx (xx%)	xx	xx (xx%)	xx
Any AE leading to withdrawal from study	xx (xx%)	xx	xx (xx%)	xx	xx (xx%)	xx
Any AE leading to death	xx (xx%)	xx	xx (xx%)	xx	xx (xx%)	xx
Action taken with study drug	xx (xx%)	xx	xx (xx%)	xx	xx (xx%)	xx
Dose Not Changed	xx (xx%)	xx	xx (xx%)	xx	xx (xx%)	xx
Dose Rate Reduced	xx (xx%)	xx	xx (xx%)	xx	xx (xx%)	xx
Dose Reduced	xx (xx%)	xx	xx (xx%)	xx	xx (xx%)	xx
Drug Interrupted	xx (xx%)	xx	xx (xx%)	xx	xx (xx%)	xx
Drug Withdrawn	xx (xx%)	xx	xx (xx%)	xx	xx (xx%)	xx
Not Applicable	xx (xx%)	xx	xx (xx%)	xx	xx (xx%)	xx
Causality	xx (xx%)	xx	xx (xx%)	xx	xx (xx%)	xx
Unlikely	xx (xx%)	xx	xx (xx%)	xx	xx (xx%)	xx
Possible	xx (xx%)	xx	xx (xx%)	xx	xx (xx%)	xx
Probable	xx (xx%)	xx	xx (xx%)	xx	xx (xx%)	xx
Severity	xx (xx%)	xx	xx (xx%)	xx	xx (xx%)	xx
Mild	xx (xx%)	xx	xx (xx%)	xx	xx (xx%)	xx
Moderate	xx (xx%)	xx	xx (xx%)	xx	xx (xx%)	xx
Severe	xx (xx%)	xx	xx (xx%)	xx	xx (xx%)	xx
Life-Threatening	xx (xx%)	xx	xx (xx%)	xx	xx (xx%)	xx
Death	xx (xx%)	xx	xx (xx%)	xx	xx (xx%)	xx

Data based on the Full analysis set. N: number of subjects in treatment group. Percentages are based on N. n, number of subjects. m, number of events. The following AEs are coded with multiple MedDRA terms and are represented as separate AEs in tables and listings: '[AE TERM 1]', '[AE TERM 2]', '[AE TERM 3]'. See listings for detailed information. SAS program: [PROGRAM NAME].sas. Run by: [USERNAME] YYYY-MM-DDTHH:MM:SS. Data extracted at: YYYY-MM-DDTHH:MM:SS

